4.2 Restricted Concomitant Medications

The dose and regimen of the following medications should not be changed from the pretreatment observation period through the completion of an examination 2 days after final administration in principle. Change of dose and regimen during this period is allowed if it is required for safety reasons. In such cases, “the reason of change” and “the details of change” should be recorded. Within 24 hours before and after first tolvaptan administration, however, the dose and regimen of restricted concomitant medications should not be changed (if changed, the subject’s participation in the trial should be discontinued).

- Therapeutic drugs for heart failure (injectables): Catecholamine preparations, human atrial natriuretic peptide preparations, phosphodiesterase 3 inhibitors, colforsin preparations, etc
- Diuretics (oral preparations and injectables)

5 Reporting of Adverse Events

5.1 Definitions

An AE is defined as any untoward medical occurrence in a patient or clinical trial subject administered a medicinal product and which does not necessarily have a causal relationship with this treatment. Adverse events would not include information recorded as medical history at screening for preplanned procedures for which the underlying condition was known and no worsening occurred. An adverse reaction is any untoward and unintended response to an IMP related to any dose administered.

A suspected adverse reaction is any AE for which there is a reasonable possibility that the IMP caused the AE.

An SAE includes any event that results in any of the following outcomes:

- Death
- Life-threatening; ie, the subject was, in the opinion of the investigator or subinvestigator, at immediate risk of death from the event as it occurred. It does not include an event that, had it occurred in a more severe form, might have caused death.
- Persistent or significant incapacity/disability or substantial disruption of the ability to conduct normal life functions
- Requires in-patient hospitalization or prolongs hospitalization
 - Hospitalization itself should not be reported as an SAE; whenever possible the reason for hospitalization should be reported.
 - Hospitalizations or prolonged hospitalizations for social admissions (ie, those required for reasons of convenience or other non-medical need) are not considered SAEs.
- Congenital anomaly/birth defect.
- Other medically significant events that, based upon appropriate medical judgment, may jeopardize the subject and may require medical or surgical intervention to prevent one of the outcomes listed above; eg, allergic bronchospasm requiring intensive treatment in an emergency room or home, blood dyscrasias or convulsions that do not result in hospitalization, or the development of drug dependency or drug abuse.

Nonserious AEs are all AEs that do not meet the criteria for a “serious” AE.

Immediately Reportable Event (IRE):

- Any SAE
- Any AE related to occupational exposure
- Potential drug induced liver injury (see [Section 5.4](#))
- Pregnancies are also defined as IREs. Although normal pregnancy is not an AE, it will mandate IMP discontinuation and must be reported on an IRE form to the sponsor. Pregnancy will only be documented in the “Adverse event” section of a CRF if there is an abnormality or complication.

Clinical Laboratory Test Value Changes: It is the investigator’s or subinvestigator’s responsibility to review the results of all laboratory tests as they become available. This review will be documented by the investigator’s or subinvestigator’s dated signature on the laboratory report. For each abnormal laboratory test result, the investigator or subinvestigator needs to ascertain if this is an abnormal (ie, clinically significant) change from the baseline for that individual subject. This determination, however, does not necessarily need to be made the first time an abnormal value is observed. The investigator or subinvestigator may repeat the laboratory test or request additional tests to verify the results of the original laboratory tests. If this laboratory value is considered medically relevant by the investigator or subinvestigator (subject is symptomatic, requiring corrective treatment or further evaluation), or if the laboratory value leads to discontinuation, and/or fulfills a seriousness criterion, this is considered an AE.

Severity: Adverse events will be graded on a 3-point scale and reported as indicated in a CRF. The intensity of an AE is defined as follows:

1 = Mild: Discomfort noticed, but no disruption to daily activity.

2 = Moderate: Discomfort sufficient to reduce or affect normal daily activity.

3 = Severe: Inability to work or perform normal daily activity.

IMP Causality: Assessment of causal relationship of an AE to the use of the IMP is defined as follows:

Related: There is a reasonable possibility of a temporal and causal relationship between the IMP and the AE.

Not Related: There is no temporal or causal relationship between the IMP and the AE.

5.2 Eliciting and Reporting Adverse Events

The investigator or subinvestigator will periodically assess subjects for the occurrence of AEs. To avoid bias in eliciting AEs, subjects should be asked the non-leading question: “How have you felt since your last visit?” All AEs (serious and nonserious) reported by the subject from informed consent to the end of trial must be recorded in source documents and CRFs provided by the sponsor.

Use medical terminology in AE reporting. Adverse events should be reported as a single unifying diagnosis whenever possible or, in the absence of a unifying diagnosis, as individual signs or symptoms. Exacerbation or disease progression should be reported as an AE only if there are unusual or severe clinical features that were not present, or experienced earlier, or not expected based on the course of the condition. If an AE that has been previously reported worsens and its severity or seriousness changes, it should be reported as a new AE in a CRF.

In addition, the sponsor must be notified immediately by e-mail of any IRE which occurred from the time of informed consent by a legal representative to the end of trial, according to the procedure outlined in [Section 5.3](#). Special attention should be paid to recording hospitalization and concomitant medications.

In a CRF, the following items should be recorded according to the procedures for preparing a CRF provided by the sponsor.

- Event name
- Date of onset (also time of onset, if possible, during hospitalization) and date of resolution
- Severity
- Seriousness (if serious, specify the details)
- IMP causality
- Action taken with the IMP
- Outcome

5.3 Immediately Reportable Events

The investigator or subinvestigator must immediately report after either the investigator, subinvestigator, or designee becomes aware of any IRE, by e-mail to the sponsor using the contact information on the cover page of this protocol.

An IRE form must be completed and sent by e-mail to the sponsor. Please note that the IRE form is NOT the “Adverse event” section of the CRF. Due regard should be paid to privacies when sending the IRE form or other documents by e-mail, etc.

Subjects experiencing SAEs should be followed until the events are resolved, stabilized, or the subject is lost to follow-up. Resolution means that the subject has returned to the baseline state of health, and stabilized means that the investigator or subinvestigator does not expect any further improvement or worsening of the subject’s condition. It is expected that the investigator or subinvestigator will provide or arrange appropriate supportive care for the subject and will provide prompt updates on the subject’s status to the sponsor.

5.4 Potential Drug Induced Liver Injury

For a subject who experiences an elevation in AST or ALT that is ≥ 3 times the upper limit of the reference range for their age and gender, a total bilirubin level should also be evaluated. If the total bilirubin is ≥ 2 times the upper limit of the reference range for their age and gender, the investigator or subinvestigator should record all these values in an IRE form and promptly report to the sponsor according to the procedure specified in [Section 5.3 Immediately Reportable Events](#).

5.5 Pregnancy

Before enrolling a female who has begun menstruation in this trial, the investigator or subinvestigator must review the guidelines about trial participation with all female subjects who have begun menstruation. The topics should generally include:

- Informed consent form
- Guidelines for the follow-up of a reported pregnancy

Before trial enrollment, the legal representative of the female subject (potential female subject) who has begun menstruation must be advised of the importance of avoiding pregnancy during trial participation and the potential risk factors for an unintentional pregnancy. The legal representative must sign an informed consent form stating that the above-mentioned risk factors and consequences were discussed with her.

A urine pregnancy test for human chorionic gonadotropin (hCG) will be performed at screening on all females who have begun menstruation. If a urine test is performed and is positive, the investigator or subinvestigator will follow up with a confirmatory serum test.

During the trial period, all female subjects and legal representatives should be instructed to contact the investigator or subinvestigator immediately if they suspect they might be pregnant.

If a subject is suspected to be pregnant before she receives the IMP, the IMP administration must be withheld until the results of serum pregnancy tests are available. If the pregnancy is confirmed, the subject must not receive the IMP and must not be enrolled in the trial. If pregnancy is suspected while the subject is taking the IMP, the IMP must be withheld immediately (if reasonable, taking into consideration any potential withdrawal risk) until the result of serum pregnancy test is known. If pregnancy is confirmed, the IMP will be permanently discontinued in an appropriate manner (eg, dose tapering if necessary for the subject's safety) and the subject will be withdrawn from the trial.

The investigator or subinvestigator must immediately notify the sponsor of any pregnancy associated with IMP exposure during the trial period and for 30 days after final IMP administration, and record the event on an IRE form and forward it to the sponsor. The sponsor will forward Pregnancy Surveillance Form(s) for monitoring the outcome of the pregnancy.

Protocol-required procedures for trial discontinuation and follow-up must be performed on the subject unless contraindicated by pregnancy (eg, x-ray). Other appropriate pregnancy follow-up procedures should be considered, if indicated. In addition, the investigator or subinvestigator must report to the sponsor, on appropriate Pregnancy Surveillance Form(s), follow-up information regarding the course of the pregnancy, including perinatal and neonatal outcome. Infants will be followed for a minimum of 6 months from the date of birth.

5.6 Procedure for Breaking the Blind

Not applicable

5.7 Follow-up of Adverse Events

For this trial, information on AEs will be collected until the follow-up examination performed 5-7 days after final IMP administration (hereinafter referred to as "the end of trial date").

After the end of trial date, an AE falling into any of categories in [Section 5.7.1](#), [Section 5.7.2](#), and [Section 5.7.3](#) will be followed as specified.

5.7.1 Follow-up of Nonserious Adverse Events

Nonserious AEs that are identified at any time during the trial period must be recorded on the “Adverse event” section of the CRF with the current status noted. If a subject has an AE or has not recovered from an AE at the end of trial date, follow-up contacts will be scheduled at least every 4 weeks until the event is resolved, stabilized, or the subject is lost to follow-up. All nonserious AEs that are ongoing at the end of trial date will be recorded as ongoing in a CRF. For any AE having been identified throughout the trial, during analysis, additional relevant medical history information may be requested to further ascertain causality (including, but not limited to, information such as risk-related behavior, family history and occupation). The follow-up information after the end of trial date will be recorded in the subject’s medical record.

5.7.2 Follow-up of Serious Adverse Events

This trial requires that subjects be actively monitored for SAEs up to the end of trial date. If a subject has an AE or has not recovered from an AE at the end of trial date, follow-up contacts will be scheduled at least every 4 weeks until the event is resolved, stabilized, or the subject is lost to follow-up.

Serious AEs that are identified or ongoing at the end of trial date must be recorded on the “Adverse event” section of the CRF and reported to the sponsor according to the reporting procedure outlined in [Section 5.3](#). All SAEs that are ongoing at the end of trial date will be recorded as ongoing in a CRF. This may include unresolved previously reported SAEs, or new SAEs. The investigator or subinvestigator will follow SAEs until the events are resolved, stabilized, or the subject is lost to follow-up. The investigator or subinvestigator will continue to report any significant follow-up information to the sponsor until the event is resolved or stabilized, or the subject is lost to follow-up with and IRE form.

5.7.3 Follow-up and Reporting of Serious Adverse Events Occurring After End of Trial Date (Last Scheduled Contact)

Any new SAE reported by the subject to the investigator or subinvestigator that occur after the end of trial date, and are determined by the investigator or subinvestigator to be related to the IMP, should be reported to the sponsor. The investigator or subinvestigator should follow SAEs identified after the end of trial date until the events are resolved, stabilized, or the subject is lost to follow-up. The investigator or subinvestigator should continue to report any significant follow-up information to the sponsor until the event is resolved or stabilized, or the subject is lost to follow-up with and IRE form.

6 Pharmacokinetic/Pharmacodynamic Analysis

6.1 Pharmacokinetic Analysis

In the pharmacokinetic analysis set (see [Section 7.2](#)), the plasma concentrations of OPC-41061 and its metabolites (DM-4103 and DM-4107) will be summarized by descriptive statistics, in the following 2 ways.

- Summarization for each compound, time point of blood sampling, and dose per unit of body weight
- Summarization for each compound, time point of blood sampling, dose per unit of body weight, and age group (young age, 6 months to less than 2 years; middle age, 2 years to less than 7 years; and old age, 7 years to less than 15 years)

Descriptive statistics to be determined are the number of subjects, mean, standard deviation, coefficient of variation, minimum, median, and maximum.

The population pharmacokinetic analysis of OPC-41061 will be separately performed and reported.

6.2 Pharmacodynamic Analysis

A pharmacodynamic analysis will be performed in the pharmacodynamic analysis set (see [Section 7.2](#)). For the items listed below, descriptive statistics (the number of subjects, mean, standard deviation, minimum, median, and maximum) of measured values and changes from baseline (immediately before tolvaptan administration) at each time point after start of administration at evaluation dose (see [Section 7.4](#)) will be determined.

As a subgroup analysis, the items will also be analyzed for each age group (young age, 6 months to less than 2 years; middle age, 2 years to less than 7 years; and old age, 7 years to less than 15 years).

The same analysis will be performed for each evaluation dose (0.05, 0.15, 0.3, and 0.5 mg/kg/day) (in the entire and each age group).

In the subgroup analysis and the analysis by evaluation dose, data collected on the day after the third day of administration at evaluation dose, the day after final administration at evaluation dose, and the day after final administration will be analyzed.

An analysis will also be performed using data collected immediately before start of administration at evaluation dose as a baseline. In addition, data will be summarized by the number of days elapsed since start of administration.

- Daily fluid intake
- Daily fluid balance
- Serum osmolality
- Serum or blood sodium concentration
- Serum or blood potassium concentration
- Urine osmolality
- Daily urine sodium excretion
- Daily urine potassium excretion
- Plasma AVP concentration

7 Statistical Analysis

7.1 Sample Size

For the primary endpoint, the required sample size was set by first setting the threshold value for assessment of efficacy, and then using binomial distribution to determine the number of subjects required to maintain a 90% or higher probability that the lower limit of the 95% CI for the percentage of subjects achieving the primary endpoint will be above the threshold value.

As reference information for the threshold value and binomial distribution parameter required to set the sample size for the trial, a threshold of 0.3 and a binomial distribution parameter of 0.5 to 0.6 were used based on interviews with clinicians, since no clinical trial results for administration of tolvaptan in pediatric patients have been obtained either in Japan or other countries.

Based on the above, the required number of subjects was calculated to be a minimum of 68 for a parameter of 0.5 and a minimum of 30 for a parameter of 0.6.

A sample size of 30 to 68 subjects was therefore considered to be appropriate, and in view of feasibility the number of subjects for the trial was set at 60.

7.2 Datasets for Analysis

The full analysis set (FAS) includes all subjects who received at least 1 dose of the IMP and have postdose data on body weight and daily urine volume.

The dose maintenance analysis set includes all subjects who received administration at same dose for at least 3 days in the full dataset.

The safety analysis set (SAS) includes all subjects who received at least 1 dose of the IMP.

The pharmacokinetic analysis set includes all subjects who received at least 1 dose of the IMP and have postdose data on drug concentration.

The pharmacodynamic analysis set includes all subjects who received at least 1 dose of the IMP and have postdose pharmacodynamic data.

7.3 Handling of Missing Data

If data on body weight and edematous symptoms cannot be obtained at assessment on the day after the third day of administration at evaluation dose, the missing data will be imputed using the last available data obtained by that day. If data on body weight on the day after the third day of administration at evaluation dose cannot be obtained, the definition of primary endpoint, “the mean daily urine volume for the 3 days of treatment at evaluation dose” ([Section 3.5.1](#)), will be changed to “the mean daily urine volume from start of administration at evaluation dose to the day on which the imputed data on body weight is obtained”.

7.4 Definition of Evaluation Dose

Of the doses administered as specified in [Section 3.2.2](#) and [Section 3.2.3](#), the dose meeting the following criteria is defined as an evaluation dose.

- 1) If sufficient increase in urine volume was obtained during the course of dose escalation, or if the dose was increased to 0.5 mg/kg/day because sufficient increase in urine volume was not obtained:
 - If the dose was not subsequently reduced, then that dose
 - If the dose was reduced without having been administered for 3 days, then the reduced dose
 - If the dose was reduced after having been administered for 3 days, then the dose before reduction

- 2) If IMP administration was discontinued before sufficient increase in urine volume was obtained during the course of dose increase:
 - The dose at final IMP administration

Other definitions of evaluation dose will be considered if necessary.

7.5 Primary and Secondary Endpoint Analyses

The following analyses will be performed in the full analysis set. As a subgroup analysis, the items will also be analyzed for each age group (young age, 6 months to less than 2 years; middle age, 2 years to less than 7 years; and old age, 7 years to less than 15 years).

The same analysis will be performed for each evaluation dose (0.05, 0.15, 0.3, and 0.5 mg/kg/day) (in the entire and each age group).

In the subgroup analysis and the analysis by evaluation dose, data collected on the day after the third day of administration at evaluation dose, the day after final administration at evaluation dose, and the day after final administration will be analyzed.

The same analysis will be performed in the dose maintenance analysis set.

Efficacy will be comprehensively assessed based on the results of primary and other endpoints.

7.5.1 Primary Endpoint Analysis

The definition of primary endpoint is presented in [Section 3.5.1](#).

The number and percentage of subjects as well as exact 95% CI based on binomial distribution will be calculated. The same calculations will be performed regarding body weight on the day after final administration at evaluation dose and the day after final administration. The number and percentage of subjects will also be calculated for each time point after the start of administration at evaluation dose.

An analysis will also be performed using data collected on the first day of administration at evaluation dose as a baseline.

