
Safety: Adverse event (AE) reporting, clinical laboratory tests, vital signs, 12-lead electrocardiogram, and pregnancy test (only for female subjects who have begun menstruation)
	

Criteria for Evaluation:
	
Primary Endpoint: The percentage of subjects who satisfy the following condition:
 
 • Body weight on the day after the third day of treatment with tolvaptan at the evaluation dose (see Section 7.4) is decreased by 1.7% or more from the weight measured before breakfast on the first day of the treatment period 
However, mean daily urine volume for the 3 days of treatment with tolvaptan at the evaluation dose must be higher than the daily urine volume for the pretreatment observation period. For subjects who discontinued treatment with tolvaptan, mean daily urine volume up until the time of discontinuation must be higher than the daily urine volume for the pretreatment observation period.
 
Secondary Endpoint(s):
 
 • Body weight • Edematous symptoms (edema [lower limbs, eyelids, etc], dyspnea, jugular venous distension, pulmonary congestion, cardiothoracic ratio, respiration rate at rest, pulse rate, and pleural effusion), central venous pressure (only subjects with central venous catheterization), and retention of pericardial effusion (only subjects requiring echocardiography to confirm retention of pericardial effusion prior to tolvaptan administration) • Daily urine volume

Statistical Methods:
	
[Statistical Methods for Primary Endpoint]
 
The number and percentage of subjects whose body weight on the day after the third day of treatment with tolvaptan at the evaluation dose is decreased by 1.7% or more from the weight measured before breakfast on the first day of the treatment period will be calculated together with exact 95% confidence intervals (CI) based on binomial distribution. The same calculations will be performed regarding body weight on the day after final tolvaptan administration. The number and percentage of subjects will also be calculated for each time

point after the start of treatment at the tolvaptan evaluation dose using body weight on the first day of administration at the evaluation dose as the baseline.

[Rationale for the Sample Size]

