## 4 Sample Size

For the primary endpoint, the required sample size was set by first setting the threshold value for assessment of efficacy, and then using binomial distribution to determine the number of subjects required to maintain a 90% or higher probability that the lower limit of the 95% confidence interval (CI) for the percentage of subjects achieving the primary endpoint will be above the threshold value.

As reference information for the threshold value and binomial distribution parameter required to set the sample size for the trial, a threshold of 0.3 and a binomial distribution parameter of 0.5 to 0.6 were used based on interviews with clinicians, since no clinical trial results for administration of tolvaptan in pediatric patients have been obtained either in Japan or other countries.

Based on the above, the required number of subjects was calculated to be a minimum of 68 for a parameter of 0.5 and a minimum of 30 for a parameter of 0.6.

A sample size of 30 to 68 subjects was therefore considered to be appropriate, and in view of feasibility the number of subjects for the trial was set at 60.

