### 8.1.1      Primary Efficacy Analysis

The number and percentage of subjects as well as the exact 95% CI based on binomial distribution will be calculated. The same calculations will be performed for body weight on the day after the final administration at the evaluation dose and the day after the final administration. The number and percentage of subjects will also be calculated for each

time point after the start of administration at the evaluation dose (the data to be summarized are from the first day of administration at the evaluation dose to the day after the final administration at the evaluation dose and follow-up period; the same shall apply hereinafter).

Analysis will also be performed using data collected on the first day of administration at the evaluation dose as the baseline.

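### Must the primary analysis state a comparison with the 30% threshold on which the trial was sized?

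*Protocol*

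**What the plan says.** Protocol 7.1 explains that "the required sample size was set by first setting the threshold value for assessment of efficacy", and that "a threshold of 0.3 and a binomial distribution parameter of 0.5 to 0.6 were used based on interviews with clinicians". The requirement is a probability of at least 90% that the lower 95% confidence limit for the primary endpoint lies above 0.3. The Synopsis and SAP 4 repeat this. SAP 4 states that "the required number of subjects was calculated to be a minimum of 68 for a parameter of 0.5", and the corresponding minimum at 0.6 is 30. Protocol 7.1 concludes: "A sample size of 30 to 68 subjects was therefore considered to be appropriate". It then sets 60 on grounds of feasibility.

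The analysis text is shorter. Under the Synopsis statistical methods, the number and percentage of responders "will be calculated together with exact 95% confidence intervals (CI) based on binomial distribution". Protocol 7.5.1 reads "The number and percentage of subjects as well as exact 95% CI based on binomial distribution will be calculated", and SAP 8.1.1 reads "The number and percentage of subjects as well as the exact 95% CI based on binomial distribution will be calculated". None of the three mentions 0.3, a null hypothesis or a success rule.

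On populations, Protocol 7.5 opens with "The following analyses will be performed in the full analysis set" and then repeats the work in the dose maintenance analysis set. Both Protocol 7.5 and SAP 8 leave the efficacy conclusion to an overall reading of the primary and other endpoints. The primary-endpoint table titles in SAP Appendix 1 and the list of changes in SAP 14 do not mention the threshold.

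**The concern.** The trial has no control group, so 30% is the only figure in the documents against which the primary response rate can be judged. The 90% probability describes a pass-or-fail event, yet no analysis section says that the event will be checked or what follows if it does not occur. Efficacy could be concluded from the overall reading with the sizing criterion unmet, and that would not depart from the plan.

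A second, smaller worry is that 60 falls short of the plan's own minimum of 68 at a true rate of 0.5, and the probability that 60 does provide is not given. Moreover, 60 is the number to receive tolvaptan (Protocol 3.3.1), while the full analysis set also requires postdose body weight and urine volume (Protocol 7.2).

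**Working it through.** **Inputs.** From Protocol 7.1: threshold 0.3; assumed true rates 0.5 to 0.6; two-sided 95% interval; target probability 90%; planned n = 60. From Protocol 7.5.1 and SAP 8.1.1: exact binomial interval.

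**Method.** The exact (Clopper-Pearson) lower limit for x responders out of n is the 0.025 quantile of a Beta(x, n − x + 1) distribution. Let c be the smallest x whose lower limit exceeds 0.3. The probability of meeting the criterion at true rate p is P(X ≥ c) with X ~ Binomial(n, p).

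**The plan's own sizes.**

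| n | c | lower limit at c | lower limit at c − 1 | true rate | P(X ≥ c) |
|---|---|---|---|---|---|
| 68 | 29 | 0.307 | 0.294 | 0.5 | 0.909 |
| 30 | 15 | 0.313 | 0.283 | 0.6 | 0.903 |

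One subject fewer gives 0.889 (n = 67, rate 0.5) and 0.864 (n = 29, rate 0.6). At 0.5, n = 66 also reaches 0.912, but 67 drops back. So 68 is the smallest size from which the target holds for every larger n examined (up to 199). Both stated minima are therefore right. Neither alternative interval reproduces both: on the same basis a Wilson interval gives 64 and 29, and a Wald interval gives 68 and 29. The interval behind the sizing is thus the exact interval that the analysis sections promise.

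**At n = 60.** c = 26, since 26/60 = 43.3% has interval 30.6% to 56.8%, while 25/60 = 41.7% has 29.1% to 55.1%.

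| true rate | P(X ≥ 26) |
|---|---|
| 0.3 | 0.0196 |
| 0.5 | 0.877 |
| 0.55 | 0.974 |
| 0.6 | 0.997 |

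At 0.5 the shortfall is 90 − 87.7 = 2.3 points, and the chance of missing the criterion is 100 − 87.7 = 12.3%. The probability reaches 90% at a true rate of about 0.51.

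**Fewer than 60 in the full analysis set.** The documents give no expected loss. If 1 to 6 subjects were lost (an assumption), the probability at 0.5 would lie between 82.5% (n = 56) and 88.1% (n = 58). It does not fall steadily, because c moves in whole subjects.

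**What the text fixes in advance.** The threshold, the statistic and the direction are stated in Protocol 7.1, the Synopsis and SAP 4. The endpoint's time point and baseline are set in Protocol 3.5.1 and SAP 6.1. Only a sentence in the analysis sections linking the reported interval to 0.3, and giving that comparison a role, is absent.

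**The case for a change.** The best case for a change is this. A comparison made by eye after the results are known is weaker than a criterion declared beforehand. The plan also yields up to 12 exact intervals for this response before any subgroup (3 time points × 2 baselines × 2 analysis sets), and nothing says which of them must clear which value. A sentence naming the full analysis set and 30% would cost no patients, data or analyses.

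Part of this stands: such a sentence would be clearer, and the sponsor may add it. It is not a needed correction, for three reasons.

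- The number cannot be picked after the fact, because it is already in the SAP. The main interval is identifiable from the endpoint definition and from Protocol 7.5 putting the full analysis set first, although SAP 8 names the two sets side by side.
- A sentence that reports met or not met next to the overall reading leaves the same conclusions open as now. Only a binding rule would close them. Whether this trial should carry one is debatable: it is open-label, uncontrolled and dose-defining, and 0.3 is introduced as a reference figure from clinician interviews. Protocol 2.1 says the plan was prepared under an agreement with the regulator, which is not available here.
- A pass-or-fail sentence could not simply be dropped in. For subjects who stop early, Protocol 3.5.1 averages urine volume up to discontinuation. SAP 6.1 averages it over treatment at the evaluation dose when that lasts less than three days. The rule would need one of these definitions, and that difference is a separate matter.

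On sample size, the objection that 60 misses 90% at 0.5 is correct, but the plan never claims otherwise.

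**Conclusion.** No change is called for. The analysis sections leave out a cross-reference to a criterion that the same documents state in advance. Any analyst following the plan will produce the interval that has to be set against 30%, and the position is plain from the count: 26 or more of 60 clears it, 25 does not. The choice of 60 is a disclosed feasibility trade-off. It costs 2.3 points of probability at the lower end of the assumed range and nothing from about 0.51 upwards.

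These figures assume that all 60 treated subjects enter the full analysis set and that the exact interval is used as planned. The conclusion also takes the overall assessment of efficacy as the sponsor's deliberate choice; the regulator's agreement, which could confirm or contradict that, was not seen.
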